4.2 Safety Population

The safety population will include all subjects who receive at least 1 dose of study drug. Subjects are categorized in the treatment group of the treatment they actually receive.

4.3 Pharmacokinetic Population

The pharmacokinetic population will include all subjects who received at least 1 dose of study drug and have at least 1 evaluable tissue concentration without a protocol deviation considered to significantly affect the pharmacokinetics.

4.4 Per Protocol Population

The per protocol population will include all subjects in the ITT who do not have pre-defined major protocol deviations that may affect the primary efficacy endpoint and have completed the study until Visit 5 (Day 57).

5. Data Handling

Unless otherwise specified, the baseline value which is not related to the efficacy analysis is defined as the last value obtained before the date and time of the first dose of study drug. Post-baseline values are defined as value obtained after the first dose of study drug.

The efficacy related baseline value (such as Total Mayo Score) is defined as the measurement taken at screening.

Change from baseline is defined as a post-baseline value minus the baseline value.

5.1 Time points and Visit Windows

Day 1 is defined as the day of first dose of treatment. Relative days after Day 1 are calculated as (assessment date – Day 1 date) + 1. Relative days prior to Day 1 are calculated as (assessment date – Day 1 date). The day prior to Day 1 is Day -1.

All data will be analyzed using nominal study visits as defined in the Study Schedule and case report form (CRF). No visit windows will be applied for summary and analysis.

Statistical Analysis Plan

Sponsor Name: Bridge Biotherapeutics, Inc.
Sponsor Protocol ID: BBT401-UC-005

5.2 Handling of Dropouts, Missing Data, and Outliers

For the primary and secondary efficacy responder analysis based on the total Mayo score, subjects with missing data will be deemed as "unresponsive". For subjects who received rescue therapy after the first dose of study drug and prior to Day 57, the response status will be deemed as "unresponsive" regardless of the Mayo score value at Day 57.

In terms of the exploratory endpoints, for the endoscopic response rate by total Mayo score, if a subject has no Mayo endoscopic subscore on Day 57, then the last post-baseline measurement prior to Day 57 will be used and the analysis will be based on the imputed value. If a subject does not have any post-baseline Mayo endoscopic subscore measurement, then the subject will be deemed as "unresponsive".

For modified Mayo remission rate at Day 57, if a subject has more than or equal to 2 questions are not answered, then the subject will be considered as "unresponsive". If a subject has only 1 question is not answered, then the last post-baseline question answered prior to Day 57 will be used to calculate the modified Mayo remission rate at Day 57.

For systemic remission rate at Day 57 based by total Mayo score, if a subject has 2 questions are not answered, then the subject will be considered as "unresponsive". If a subject has only 1 question is not answered, then the last post-baseline question answered prior to Day 57 will be used to calculate the systemic remission rate at Day 57.

For the clinical remission at Day 112, the percentage of subjects with sustained remission on Day 112, and the clinical response rate at Day 112 which are all based on the total Mayo score, if a subject has more than or equal to 3 questions are not answered, then the subject will be considered as "unresponsive". If a subject has less than 3 questions are not answered, then the last post-baseline question(s) answered prior to Day 112 will be used to calculate the total Mayo score and information relevant to derive those Day 112 related exploratory endpoints.

For the UCEIS exploratory endpoint, if a subject has 1 unanswered UCEIS descriptor for the Day 57 visit, the last post-baseline value for the UCEIS descriptor prior to Day 57 will be used to calculate the final index score and to classify the achievement of endoscopic response by Day 57. If a subject has more than 1 unanswered UCEIS descriptor for the Day 57 visit, the last post-baseline value of the UCEIS index score prior to Day 57 will be used to classify the achievement of endoscopic response by Day 57. If a subject does not have any post-baseline measurement, then the subject will be deemed as "unresponsive".

In terms of handling missing/incomplete IBDQ, the following rule (as shown in the table below) will be followed before any imputation to be taken into a place:

	Number of Missing Values				Comments /Actions
	Subscore 1	Subscore 2	Subscore 3	Subscore 4	
Scenario A	0	0	0	0	You can compute 4 subscores and the full IBDQ

CONFIDENTIAL

Page 10 of 30

Statistical Analysis Plan

Sponsor Name: Bridge Biotherapeutics, Inc.
Sponsor Protocol ID: BBT401-UC-005

Scenario B	1	0	0	0	You can compute both the full IBDQ and the 4 subscores, by replacing the missing value with the average mean (computed on the data available for its own subscore)
Scenario C	1	1	1	1	You can compute both the full IBDQ and the 4 subscores, by replacing the missing values with the average means (each one computed on the data available for its own subscore)
Scenario D	2	0	0	0	You can compute the full IBDQ by replacing the 2 missing values with the average mean (computed on the data available for its own subscore). You can compute only 3 subscores
Scenario E	2	1	0	1	You can compute the full IBDQ by replacing the missing values with the average means (each one computed on the data available for its own subscore). You can compute only 3 subscores
Scenario F	2	1	1	1	You cannot compute the full IBDQ (more than 4 missing values). You can compute only 3 subscores
Scenario G	2	2	0	0	You cannot compute the full IBDQ because in more than one subscore there are 2 missing values (even though the total missing value is not exceeding 4). You can compute only 2 subscores.
Scenario H	0	0	3	0	You cannot compute the full IBDQ because there is one subscore with more than 2 missing values. You can compute only 3 subscores.

If the IBDQ missing value scenario is not covered via the process described above, the last post-baseline measurement will be used and analysis will be based on the imputed value.

Missing histopathology data will be considered as non-remission when analysis is performed.

Missing biomarkers data will not be imputed.

Handling of missing/incomplete concomitant medication start/stop date will be documented in Section 6.4.2 Previous and Concomitant Medication.

Handling of missing/incomplete AE start/stop date will be documented in Section 6.7.2 Adverse Events.

6. Statistical Methods

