7.5. Guidelines, Study Assessments, and Procedures During the Coronavirus Disease-19 Pandemic

In view of the coronavirus disease -19 (COVID-19) worldwide pandemic, the safety and wellbeing of study subjects is of primary importance. Study sites must comply with local public health rules.

Although every effort should be made to follow the protocol, subject safety is paramount and the investigator should continue to reassess the risks and benefits of continued study participation for each subject.

If a subject is diagnosed with COVID-19 or is suspected to have COVID-19, they should follow the local treatment and quarantine guidances.

- All diagnoses, procedures, assessments, dosing interruptions, and sequelae should be recorded in the electronic case report form (eCRF).
- Adverse events and SAEs should be reported in accordance with instructions in [Appendix 1](#). If an AE or SAE related to COVID-19 is reported, the investigator should determine whether study drug administration should continue, be interrupted, or stopped.

If a subject is unable to attend study site visits and/or receive study drug, site staff should keep contact with the subject, preferably via telephone calls, to maintain awareness of subject status. If the subject is unable to attend the site, the following options may be considered:

- Subjects may be visited at their home by study staff or other trained professionals (where possible due to social distancing requirements).
- Visits may be performed by telephone or telemedicine to provide continuous medical care and oversight and to identify AEs.

- Blood samples may be collected and analysed at an alternative healthcare facility, at the discretion of the investigator. Although results of these analyses may not necessarily be collected or documented in the study database, it will allow the investigator to assess subject safety.
- If the endoscopy at the end-of-treatment visit can not be performed, the partial Mayo score may be collected by telephone or telemedicine (preferred).

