8.4. Efficacy Analyses

8.4.1. Primary and Secondary Efficacy Analysis

All subjects in the intent-to-treat population will be included in the primary and secondary efficacy analyses. Descriptive summaries will be presented for clinical response, clinical remission, and endoscopic remission rates. The estimate and 95% confidence interval (CI) of clinical response, clinical remission, and endoscopic remission rates at Day 57 will be calculated using the exact binomial method for each treatment. The Fisher's exact test will be used to evaluate any differences between treatments.

Missing data will be deemed as "unresponsive". If any event that was not initially anticipated demands to reconsider data handling, then the method of handling the relevant data will be established in the statistical analysis plan.

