6.6 Efficacy

6.6.1 Primary Efficacy Analysis

The primary efficacy endpoint is the clinical response rate at Day 57, as measured by a reduction of ≥ 3 points and $\geq 30\%$ improvement from baseline of total Mayo score, which includes a decrease in rectal bleeding subscore of ≥ 1 point or an absolute rectal bleeding subscore ≤ 1 . Centrally read Mayo endoscopic subscores will be used to evaluate the objectives of the study.

The stool frequency and rectal bleeding subscores will use the average of the last 3 non-missing assessments recorded in the subject diary. If an endoscopy is performed, the average of the last 3 non-missing assessments recorded in the subject diary prior to bowel preparation should be used. If the subscore is not an integer, the subscore should be rounded to the nearest integer. Subjects with missing values will be considered as unresponsive as described in Section 5.2.

Total Mayo Score will be calculated based on the response achieved from all 4 subscores ranged from 0-3 each out of a total sum of 12.

For example: If stool frequency = 2, rectal bleeding = 1, physician's global assessment = 2 and findings on endoscopy = 2 then total mayo score is 7 ($2+1+2+2=7$).

The percentage of improvement at day 57 is calculated as:

$((\text{Baseline Sum of the Total Mayo Score} - \text{Day 57 Sum of the Total Mayo Score}) / \text{Baseline Sum of the Total Mayo Score}) \times 100\%$.

Subjects with a reduction of ≥ 3 points and $\geq 30\%$ improvement from baseline of total Mayo score as well as a decrease in rectal bleeding subscore of ≥ 1 point or an absolute rectal bleeding subscore ≤ 1 will be considered as slowing a clinical response at Day 57.

Statistical Analysis Plan

Sponsor Name: Bridge Biotherapeutics, Inc.
Sponsor Protocol ID: BBT401-UC-005

The number and proportion of subjects with the 95% confidence interval (CI) of clinical response rate at Day 57 will be calculated using the exact binomial method for each treatment. The Fisher's exact test will be used to evaluate any differences between treatments at Day 57 and will be summarised for the induction phase by treatment group for the ITT Population. No adjustments will be made for multiple comparisons.

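### A missing Day 57 endoscopy scores a subject as unresponsive even when the other three Mayo subscores already guarantee a clinical response

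*SAP*

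**What the plan says.** **Missing-data rule.** SAP 5.2: "For the primary and secondary efficacy responder analysis based on the total Mayo score, subjects with missing data will be deemed as" unresponsive. SAP 6.6.1 repeats it for the primary endpoint: "Subjects with missing values will be considered as unresponsive as described in Section 5.2". Protocol 8.4.1 has the same rule: "Missing data will be deemed as" unresponsive.

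**Score.** SAP 6.6.1: "Total Mayo Score will be calculated based on the response achieved from all 4 subscores ranged from 0-3 each". Neither document defines missing data subscore by subscore. That one missing subscore makes the subject unresponsive follows from this derivation.

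**Response.** SAP 6.6.1 defines it "as measured by a reduction of ≥ 3 points and" at least 30% improvement from the baseline total, together with "a decrease in rectal bleeding subscore of ≥ 1 point or an absolute rectal bleeding subscore ≤ 1".

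**Foreseen gap.** Protocol 7.5: "If the endoscopy at the end-of-treatment visit can not be performed, the partial Mayo score may be collected by telephone or telemedicine (preferred"). Such a subject can stay in the ITT denominator, because SAP 4.1 asks for only one post-baseline Mayo score and Appendix 11 of the protocol schedules a partial score at Day 29. Appendix 11 has no endoscopy between screening and Day 57.

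**Partial data elsewhere.** SAP 5.2 carries forward one missing item for modified Mayo remission at Day 57 and up to two for the Day 112 endpoints. It makes no use of partial data for the primary endpoint.

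**The concern.** The plan collects stool frequency, rectal bleeding and physician's global assessment (PGA) from a subject whose Day 57 endoscopy could not be done. The primary analysis then ignores them. Non-responder imputation is normally justified because the outcome is unknown. Here it is also applied to subjects whose outcome is settled: each subscore has a ceiling of 3, and in some subjects the three observed subscores have improved enough that no endoscopic value could undo the response.

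With 12 subjects per arm and exact methods, one wrongly classified subject is visible in the response rate, its confidence interval and the Fisher test.

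**Working it through.** **Inputs.** Subscores run from 0 to 3 (protocol 7.1.3). Entry requires total ≥6, endoscopy ≥2, bleeding ≥1 and stool frequency ≥1 (protocol 4.1). The response definition is in SAP 6.6.1. There are 12 subjects per arm (SAP 2.2). The documents give no expected response rate, power or missing-endoscopy rate, so there is no planned figure to reproduce. The SAP's worked total, 2+1+2+2 = 7, is correct.

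**Step 1, the bound.** Reduction = baseline total − Day 57 total. A higher endoscopic subscore can only make this smaller, and it does not enter the bleeding condition. If the definition is met with endoscopy = 3, it is met at 0, 1 and 2 as well.

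**Step 2, examples** (order: stool, bleeding, PGA, endoscopy).
- *Certain.* Baseline 2+2+2+3 = 9; Day 57 0, 0, 1, missing. Worst total 0+0+1+3 = 4. Reduction 9−4 = 5, and 5/9 = 56%. Bleeding is down 2. Response at every endoscopic value; the SAP records failure.
- *Certain.* Baseline 2+2+2+2 = 8; Day 57 0, 0, 0, missing. Worst total 3. Reduction 5, and 5/8 = 62.5%.
- *Undetermined.* Baseline 2+2+2+2 = 8; Day 57 1, 1, 1, missing. With endoscopy 2 the total is 5, a reduction of 3 (37.5%), which is a response. With endoscopy 3 the total is 6, a reduction of 2, which is not.

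**Step 3, fall needed for certainty.** The required reduction is max(3, 30% of baseline rounded up): 3 points for totals 6 to 10, 4 for 11 or 12. Add 3 − baseline endoscopy. The fall in stool + bleeding + PGA must then be:

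| Baseline endoscopy | Total 6–10 | Total 11–12 |
|---|---|---|
| 3 | ≥3 | ≥4 |
| 2 | ≥4 | ≥5 (total 11 only) |

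The bleeding condition must also hold.

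**Step 4, enumeration.** Stool 3 × bleeding 3 × PGA 4 × endoscopy 2 = 72 baseline profiles. Five have totals below 6, leaving 67. Day 57 with endoscopy missing has 4³ = 64 profiles, and 67 × 64 = 4,288 pairs.

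| Status with endoscopy missing | Pairs | Share |
|---|---|---|
| Certain responder | 841 | 19.6% |
| Undetermined | 1,240 | 28.9% |
| Certain non-responder | 2,207 | 51.5% |

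All 67 baselines have at least one certain-responder profile. The pairs are unweighted, so the shares are not probabilities.

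**Step 5, scope.** If bleeding is the missing subscore, certain responders number 0, because a value of 3 always fails the bleeding condition. Certain clinical remission with any one subscore missing: 0. Endoscopic remission needs the endoscopy itself.

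**Step 6, size.** One subject is 1/12 = 8.3 points. Fisher's exact test, two-sided, with assumed counts: 7/12 vs 2/12 gives p = 0.089. Adding one responder to the active arm (8/12 vs 2/12) gives p = 0.036. Adding one to each arm (8/12 vs 3/12) gives p = 0.0995. The 0.05 level is also an assumption; the SAP states only 95% intervals.

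**Step 7, direction.** Suppose a fraction *m* of endoscopies is missed in each arm, unrelated to outcome. With true rates p_T and p_C, the present rule gives a difference of (1−m)(p_T − p_C), shrunk toward zero. Crediting certain responders, whose shares are c_T and c_C, adds back m(c_T − c_C).

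**The case against.** **The rule is pre-specified, simple and the same in protocol and SAP.** This stands. A reader might infer that protocol 7.5 and SAP 5.2 conflict. They do not: one permits a partial score to be collected, the other says how an incomplete total is classified. With equal missingness across arms the rule shrinks the difference and does not create a false positive.

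**The sensitivity analysis may cover it.** SAP 6.6.3 plans one on this endpoint, with its rules redacted. They may deal with partly missing scores. The primary result would still follow SAP 5.2, so the remaining question is which rule is primary.

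**Larger figures are tempting but unsupported.**
- Of the 1,046 pairs that respond if endoscopy is unchanged from baseline, 841 (80%) are certain. That is a favourable denominator: 841 is 40% of the 2,081 (841 + 1,240) pairs that could be responses at some value, and 20% of all pairs.
- One or two missed endoscopies per arm might be read as 8 to 17 points. That treats every such subject as a certain responder.
- A loss falling mainly on the more effective arm depends on endoscopies being missed equally across arms. Otherwise the direction is open.

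**Remote scores may differ from site scores.** Protocol 7.1.3 wants PGA from the investigator who has observed the subject, and the Mayo appendices say it takes account of physical findings. This stands: the response is certain only given the recorded subscores.

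**The data are used elsewhere.** The partial Mayo score enters a repeated-measures model and symptomatic remission needs no endoscopy (SAP 6.6.5). True, but neither is the primary endpoint.

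**An unrestricted worst-value rule would reach too far.** Visit 5 is also the early-termination visit, and SAP 5.1 applies no visit windows. An early withdrawal could be counted as a Day 57 responder. This objection shapes the fix.

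**Conclusion.** The concern holds in a limited form. For the primary endpoint, the stated rule records some responses as failures although the observed subscores settle them, and no unredacted text corrects this. The protocol itself foresees the circumstance.

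The mechanism rests on the 0-to-3 range, the response definition and the reading that one missing subscore makes the total missing. Its size is 8.3 points per certain responder in a 12-subject arm. How many there will be cannot be estimated from the documents and may be none. The Fisher results are illustrations on assumed counts.

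Clinical remission and endoscopic remission are unaffected. In an exploratory study without a formal sample-size assessment, this is a cheap improvement worth making, not a flaw that invalidates the analysis.

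**What to change.** Add to SAP 5.2, and align 6.6.1:

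> For clinical response at Day 57, if only the endoscopic subscore is missing and the other three subscores were obtained within the protocol Day 57 window, set the endoscopic subscore to 3. If all parts of the definition are met, the subject is a responder; otherwise unresponsive.

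- Leave the existing rescue-therapy override in SAP 5.2 unchanged.
- List the change from protocol 8.4.1 in SAP section 7. The protocol's allowance for revised data handling ("If any event that was not initially anticipated demands to reconsider data handling") is a weak basis, because protocol 7.5 anticipates missed endoscopies.
- Report the present rule, missing equals unresponsive, as a sensitivity analysis.
- Flag in the report each subject classified this way and whether the subscores, PGA included, were collected remotely.

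**Cost.** Edits in three SAP sections, one derivation step and one extra analysis. The rule departs from the simplest non-responder imputation and relies on remotely collected subscores. Given the recorded subscores it cannot credit a false responder, and undetermined subjects stay unresponsive.

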5.6. Rescue Therapy

A rescue treatment is defined as any procedure or medication (new medications or medications that have been increased in dose) used for the treatment of new or persistent symptoms of UC.

If a subject who does not exhibit a clinical response experiences worsening of disease (ie, worsening of clinical status or symptoms of UC that require rescue treatment) or disease relapse, study drug must be discontinued, and subjects should be treated as clinically appropriate with conventional treatments for active disease, as determined by the investigator. These subjects should continue in the study for safety assessments but will be considered treatment failures with respect to the intent-to-treat population.

A subject will be considered to have disease relapse when they meet all of the following criteria:

- an increase in UC disease activity after achievement of a clinical response, defined as an increase from nadir or Day 57 in partial Mayo score of ≥ 2 points and an absolute partial Mayo score ≥ 4 points, and
- an endoscopic subscore of ≥ 2 points, and
- exclusion of other causes of increased disease activity that are unrelated to UC (eg, infections or changes in medication).

The date and time of rescue medication administration as well as the name and dosage regimen of the rescue medication must be recorded.

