8.4.2. Exploratory Efficacy Analysis

All subjects in the intent-to-treat population will be included in the exploratory efficacy analysis. The estimate and 95% CI of endoscopic response rate and histological improvement at Day 57, and clinical response rate and the percentage of subjects with clinical remission at

Day 112 will be calculated using the exact binomial method for each treatment. Actual values and change from baseline in Mayo scores, UCEIS scores, IBDQ total score, C-reactive protein, and faecal calprotectin over time will be summarised descriptively. No formal hypothesis will be tested on the exploratory efficacy endpoints.

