6.6.5 Exploratory Analysis

- **Endoscopic response rate by Day 57, as defined by a ≥ 2 -points reduction from baseline in UCEIS score via central reading.**

The UCEIS score will be calculated as the sum of the scores of all descriptors. The higher the score, the worse the UC. Baseline total UCEIS score minus Day 57 UCEIS score will be used to calculate the number of subjects who have a ≥ 2 points reduction. With a difference ≥ 2 points will be considered as endoscopic response. Missing value will be imputed based on the description from Section 5.2.

Statistical Analysis Plan

Sponsor Name: Bridge Biotherapeutics, Inc.
Sponsor Protocol ID: BBT401-UC-005

The actual and change from baseline will be presented. The number and proportion of subjects with the 95% CI of endoscopic response rate at Day 57 will be calculated using the exact binomial method for each treatment. The Fisher's exact test will be used to evaluate any differences between treatments at Day 57 and will be summarised for the induction phase by treatment group for ITT Population.

- **Endoscopic response rate at Day 57, as defined by a reduction of ≥ 1 grade in the Mayo endoscopic subscore**

The Mayo endoscopic subscore will be based on Part 4 of the total Mayo score - "Investigator-reported Findings on endoscopy". The change in endoscopic score is calculated as the difference between the baseline and Day 57 scores. A difference of ≥ 1 grade is considered as endoscopic response. Missing values will be imputed based on the description from Section 5.2.

The number and proportion of subjects with the 95% CI of endoscopic response rate at Day 57 will be calculated using the exact binomial method for each treatment. The Fisher's exact test will be used to evaluate any differences between treatments at Day 57 and will be summarised for the induction phase by treatment group for ITT Population.

- **Modified Mayo remission rate at Day 57, as defined by a $\text{mMCS} \leq 2$, $\text{RBS}=0$, $\text{mESS} \leq 1$, $\text{SFS}=0$ or (1 if at least 1 point drop from baseline)**

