The modified Mayo remission will be based on the Total Mayo Score with all the following 4 conditions are satisfied: 1. $\text{mMCS} \leq 2$, and 2. Rectal Bleeding Score=0, and 3. $\text{mESS} \leq 1$, and 4. Stool Frequency Score=0 or (1 if at least 1 point drop from baseline), where mMCS will be collected in the Modified Mayo Score form as the sum of RBS , mESS and SFS . Missing values will be imputed based on the description from Section 5.2.

The number and proportion of subjects with the 95% CI of modified Mayo remission rate at Day 57 will be calculated using the exact binomial method for each treatment. The Fisher's exact test will be used to evaluate any differences between treatments at Day 57 and will be summarised for the induction phase by treatment group for ITT Population.

- **Symptomatic remission rate at Day 57, as defined by $\text{RBS}=0$, $\text{SFS}=0$**

The symptomatic remission rate at Day 57 will be based on the Rectal Bleeding Score =0 and Stool Frequency Score=0 from Total Mayo Score. Missing values will be imputed based on the description from Section 5.2.

Statistical Analysis Plan

Sponsor Name: Bridge Biotherapeutics, Inc.
Sponsor Protocol ID: BBT401-UC-005

The number and proportion of subjects with the 95% CI of symptomatic remission rate at Day 57 will be calculated using the exact binomial method for each treatment. The Fisher's exact test will be used to evaluate any differences between treatments at Day 57 and will be summarised for the induction phase by treatment group for ITT Population.

- **Inflammatory Bowel Disease Questionnaire (IBDQ) total score, as measured by change from baseline**

The IBDQ is a health-related quality-of-life (HRQoL) tool measuring bowel, systemic, emotional, and social function. Scores for each question range between 1 and 7, reflecting poor to good HRQoL, for a range of possible total scores from 32 to 224. In terms of the 4 aspects of patients live and their corresponding questions, it is summarised in the following table.

Aspects	Questions	Range of Score
Bowel	1, 5, 9, 13, 17, 20, 22, 24, 26, 29	10 to 70
Systemic	2, 6, 10, 14, 18	5 to 35
Emotional	3, 7, 11, 15, 19, 21, 23, 25, 27, 30, 31, 32	12 to 84
Social Function	4, 8, 12, 16, 28	5 to 35
Total Score	1~32	32 to 224

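### The SAP's rescue rule sits only under the primary and secondary total-Mayo responder analyses, so a rescued subject assessed at Day 57 can count as a success on exploratory ITT responder endpoints, contrary to Protocol 5.6

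*SAP*

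**What the plan says.** **Protocol 5.6 (Rescue Therapy).** The rule applies to a subject without a clinical response whose disease worsens so that rescue is needed, or who relapses. Study drug stops, and then: "These subjects should continue in the study for safety assessments but will be considered treatment failures with respect to the intent-to-treat population". No endpoint is singled out or exempted.

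**Protocol 8.4.2.** The exploratory endpoints use the same population: "All subjects in the intent-to-treat population will be included in the exploratory efficacy analysis".

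**SAP 5.2.** The first paragraph opens: "For the primary and secondary efficacy responder analysis based on the total Mayo score, subjects with missing data will be deemed as 'unresponsive". Its next sentence covers subjects given rescue therapy after the first dose and before Day 57, for whom "the response status will be deemed as 'unresponsive' regardless of the Mayo score value at Day 57". A new paragraph then turns to the exploratory endpoints. The rules for Mayo endoscopic response, modified Mayo remission, symptomatic remission (there called systemic remission) and UCEIS response all concern missing items. None mentions rescue.

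**SAP 6.6.5.** The four Day 57 responder endpoints are scored from the Day 57 values in the ITT population. For UCEIS: "With a difference ≥ 2 points will be considered as endoscopic response". For symptoms: "The symptomatic remission rate at Day 57 will be based on the Rectal Bleeding Score =0 and Stool Frequency Score=0 from Total Mayo Score". Each gets an exact 95% CI and a Fisher test. Section 5.2 is cited for missing values only.

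**SAP Section 7.** The listed changes in planned analysis do not include any narrowing of the protocol's failure rule.

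**The concern.** The protocol's rule belongs to the population, while the SAP's rule belongs to a group of endpoints. A programmer who follows the SAP as laid out would set rescued subjects to non-response for the primary and secondary responder analyses, and would score the exploratory endpoints on whatever values exist at Visit 5.

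Study drug has been stopped in the subjects covered by Protocol 5.6, so a good score recorded after rescue may reflect the rescue treatment. The same subject at the same visit could be a failure in one table and a success in the next. The treatment comparison would shift towards whichever arm had more rescued subjects meeting the endpoint. With 12 subjects per arm, one or two misclassified subjects are visible in the results.

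**Working it through.** There is no power calculation or planned rate to reproduce. The check is first a comparison of texts and then an illustration of size.

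**1. Does the SAP rescue rule reach each Day 57 exploratory responder endpoint in SAP 3.3?**

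| Endpoint | By placement in SAP 5.2 | By wording (response status, Mayo score) |
|---|---|---|
| UCEIS response | Not covered | Not covered; UCEIS is not a Mayo score |
| Mayo endoscopic response | Not covered | Arguable; 5.2 ties it to the total Mayo score |
| Modified Mayo remission | Not covered | Arguable; 6.6.5 bases it on the total Mayo score |
| Symptomatic remission | Not covered | Arguable; 6.6.5 takes it from the total Mayo score |

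**2. Can one subject be split across tables?** Take a subject rescued before Day 57 who afterwards has stool frequency 0, rectal bleeding 0, PGA 0 and endoscopy 1, with screening endoscopy 2 or 3 and UCEIS down by at least 2.

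- Clinical response and clinical remission: failure, by the rescue rule.
- Mayo endoscopic response: the drop is 2 − 1 = 1 or 3 − 1 = 2, so success.
- UCEIS response: success.
- Modified Mayo remission: score 0 + 0 + 1 = 1 (limit 2), bleeding 0, endoscopy 1, stool frequency 0, so success.
- Symptomatic remission: bleeding 0 and stool frequency 0, so success.

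**3. Which endpoints need an endoscopy?** The schedule (Protocol Appendix 11) has no post-baseline endoscopy before Visit 5. Without one at Visit 5, SAP 5.2 already makes both endoscopic responses failures. Symptomatic remission needs only the two diary-based items, and if one is missing the last post-baseline answer is carried forward.

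**4. Size.** Planned arm size is 12 (Protocol 3.1, SAP 2.2), taken here as all in the ITT population. One subject is 1/12 = 8.3 points.

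The documents give no rescue rate, so the following are assumptions: 2 to 4 of 12 rescued on placebo, 1 to 2 of 12 on an active arm, and a proportion q = 0.25 to 0.75 of rescued subjects meeting the endpoint.

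- Inflation of the placebo rate = rescued × q / 12: from 2 × 0.25 / 12 = 4.2 points to 4 × 0.75 / 12 = 25 points.
- Shrinkage of the active-placebo difference = (rescued on placebo − rescued on active) × q / 12:

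| Placebo, active rescued | q = 0.25 | q = 0.75 |
|---|---|---|
| 2, 2 | 0 | 0 |
| 2, 1 or 3, 2 | 2.1 | 6.3 |
| 3, 1 or 4, 2 | 4.2 | 12.5 |
| 4, 1 | 6.3 | 18.8 |

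The range is 0 to 19 points. With the imbalance reversed, for example 1 on placebo and 2 on active, the result is (1 − 2) × q / 12 = −2.1 to −6.3 points, so the difference is inflated.

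**5. Effect on the Fisher test (two-sided, assumed counts, active v placebo).**

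- One rescued placebo subject counted as a success: 6/12 v 0/12, p = 0.014, becomes 6/12 v 1/12, p = 0.069.
- One rescued active subject counted as a success: 4/12 v 0/12, p = 0.093, becomes 5/12 v 0/12, p = 0.037.

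**The case against.** **The rescue sentence may be general.** It has its own subject and does not repeat the restriction to primary and secondary analyses. A reader might infer that all four exploratory endpoints are plainly outside it, but the documents do not settle that. Its wording could be stretched to the three Mayo-based endpoints, and only UCEIS is clearly outside. This stands as a limit on the claim. It does not remove the problem, because the sentence's position and the switch of paragraph after it point the other way, and two programmers could differ.

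**The protocol rule still applies.** The SAP is silent and states no contrary rule. That is true, but the SAP is what gets programmed, and following it as placed gives a result contrary to Protocol 5.6.

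**Rescued subjects may have no usable scores.** Protocol 5.6 keeps them in for safety assessments and does not promise efficacy assessments. Visit 5 doubles as the early-termination visit, and SAP 5.1 analyses by nominal visit without windows, so the recorded scores may predate rescue. A reader might infer that every rescued subject contributes a favourable score; the documents do not support that. They do allow for some: the SAP's own override of the Day 57 Mayo score presupposes that such scores can exist, and the visit includes endoscopy, Mayo and UCEIS.

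**The endpoints are exploratory.** Protocol 8.4.2 plans no formal testing of them, no alpha is stated, and the sample size has no formal basis. Crossing 0.05 therefore decides nothing. The SAP nevertheless attaches a Fisher test to each endpoint.

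**The redacted sensitivity rules** (SAP 6.6.3) cannot close the gap, since that section covers only the primary endpoint and clinical remission.

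**Conclusion.** The point holds in a limited form. The protocol's failure rule has no endpoint limit. The SAP's rule is silent for UCEIS response and, by placement, for Mayo endoscopic response, modified Mayo remission and symptomatic remission, with the last three open to argument. Misclassification needs a rescued subject who has efficacy assessments after rescue and meets the criterion.

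Under the stated assumptions the active-placebo difference shrinks by 0 to 19 points. The upper end is an extreme corner: 4 v 1 rescued, 75% meeting the endpoint. A single q is also applied to endpoints of differing stringency. A reader might infer that the error always dilutes the drug effect; it does not, since equal rescue gives no bias in the difference and more rescue on active inflates it.

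The conflict concerns the subjects both rules cover: Protocol 5.6 speaks of worsening without response, or relapse, while SAP 5.2 speaks of any rescue before Day 57. The primary and clinical remission analyses are unaffected. The sponsor should correct this, but it does not threaten the trial's main result.

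**What to change.** In SAP 5.2, move the rescue sentence ahead of the endpoint-specific paragraphs and make it general. Suggested text:

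> For every Day 57 responder endpoint in the ITT population (primary, secondary and exploratory, including UCEIS response, Mayo endoscopic response, modified Mayo remission and symptomatic remission), subjects who received rescue therapy after the first dose and prior to Day 57 are unresponsive, regardless of observed or imputed values.

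Keep the existing timing, prior to Day 57. Tying the rule to rescue before the assessments would miss a subject assessed at early termination and rescued afterwards. Naming all secondary endpoints also removes doubt about endoscopic remission, which rests on a subscore and not on the total Mayo score.

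Refer to the rule from each of the four endpoints in SAP 6.6.5. Apply the same principle to Day 57 histologic remission and, for rescue before Day 112, to the Day 112 remission, sustained remission and response endpoints, none of which now has such a rule. If the sponsor intends the exploratory endpoints to be exempt, list and justify that departure from Protocol 5.6 in SAP Section 7.

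The cost is one sentence moved and widened, a few cross-references, reuse of the Day 57 rescue flag in programming, and a matching flag for rescue before Day 112. Exploratory rates may come out slightly lower.
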